8. DATA REPORTING / REGULATORY REQUIREMENTS

The Kaiser Permanente of Northern California study team will oversee all adverse events with a designated Data and Safety Monitoring Board. This board will include [name] (biostatistician), [name] (exercise interventionist), [name] (gastro oncologist) and study liaison.

9. STATISTICAL CONSIDERATIONS

9.1 Study design:

This randomized controlled trial of resistance training intervention in colon cancer patients receiving chemotherapy consists of two arms: an in-person and telephone-based intervention to promote home-based resistance training, and a wait-list, control group. After consent and baseline visit measurements, randomization assignment will utilize a covariate adaptive randomization procedure which ensures that equal numbers of patients are assigned to each study arm and that the two arms remain balanced on five key characteristics: site of participation [Kaiser Permanente vs Penn State vs Dana-Farber]; gender [male vs female]; cancer stage [stage II vs stage III], and duration of chemotherapy [3 months vs 6 months]; planned chemotherapy regimen [FOLFOX vs CAPOX vs capecitabine vs 5-FU/LV]. This randomization method (also known as the minimization method) has been demonstrated to outperform simple randomization or stratified randomization in terms of achieving balanced groups, particularly in smaller trials with multiple important prognostic factors.

The primary objective of this trial is to compare the effect of a RT intervention versus a wait-list control on chemotherapy dose reductions, dose delays, early discontinuation of chemotherapy and treatment-related toxicity. The secondary objective is to compare the effect of the intervention versus wait-list control on changes in inflammatory biomarkers, and the tertiary objective is to compare pre and post intervention pharmacokinetics of 5-FU and oxaliplatin. The d3 Creatine objective is to compare the effect of a RT intervention versus a wait-list control on d3 creatine muscle mass at 6 months.

9.2 Sample size, accrual time and study duration:

One hundred and eighty (180) participants will be recruited and randomized over a total of 3.5 years. Patient involvement and data collection will last approximately 6 months.

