To examine differences in dose reductions, dose delays and early stoppage for chemotherapy and the total combined number of moderate and severe chemotherapy-associated toxicities between intervention group and waitlist controls.

2. Secondary Objectives:

- a. To examine specific inflammatory markers (e.g. CRP, IL-6, TNF- α receptor II [TNF-RII]) in relation to baseline MM and fat mass (FM) and examine differences in changes in inflammatory markers between intervention group and waitlist controls. Inflammatory markers and body composition will be measured pre and post intervention.
- b. To examine the impact of RT induced body composition changes on the pharmacokinetics (PK) of 5-FU and oxaliplatin between baseline and 4 months of RT.

3. d3 Creatine Objectives

- a. To test whether resistance training during chemotherapy (v. control) increases d3 creatine muscle mass at 6 months.

- b. To evaluate the association of d3 creatine muscle mass with changes in functional status and strength during chemotherapy.
- c. To evaluate the association of d3 creatine muscle mass with chemotherapy toxicity and relative dose intensity.
- d. To evaluate the association of d3 creatine muscle mass with cancer-related biomarkers, including inflammation, CEA levels and cardiometabolic risk factors.

BACKGROUND

1.1 Colon cancer epidemiology and prognosis by stage:

Colorectal cancer is the 4th most common in the United States, with an estimated 134,490 individuals being diagnosed in 2016, 71% located in the colon (versus rectum)². Unfortunately, more than 49,190 individuals die from the disease annually, making colorectal cancer the second leading cause of cancer death in the United States. Surgery is the primary modality of management for colon cancer, and a ‘curative intent’ resection occurs in 80–85% of patients with non-metastatic disease (stages I-III). The benefit of adjuvant therapy has been consistently shown in multiple clinical trials, although the 5-year disease free survival for stage III disease is only 70%³.

1.2 Adjuvant chemotherapy and dosing:

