3.6.1 From Section D. Study overview of the original KPNC application approved 2017

3. How many participants will be enrolled in this study, or how many electronic records or medical records will be used? Provide your best estimate if you are not sure

Number of KPNC participants or records:	Approximately 115 participants to be enrolled
Records used:	Approximately 7500 KPNC records used
Number of non-KPNC participants or records:	Approximately 65 participants enrolled
Total number of participants or records:	Approximately 180* participants enrolled

**Due to the impact of the COVID-19 pandemic on the study, we estimate that the total number of participants will be within the range of 10% above the original total of 180 participants.*

3.7 Enrollment and baseline testing:

Eligible participants who agree to participate will be scheduled for their first intervention visit at the earliest possible chemotherapy visit but by the third infusion visit. See Table 3 for details regarding the enrollment window based on the specific chemotherapy regimen

Table 3. Chemotherapy Regimens and Timeline

WEEK

Regimen name & drugs	Cycle	# cycles	1	2	3	4	5	6	7	8	9	10	11	12	13	14	15	16	17	18	19	20	21	22	23	24	25	26	27	28	29	30	31	32												
mFOLFOX 6 - 3 months Oxaliplatin, Leucovorin, 5FU	14 days	6 cycles	IV		IV		IV		IV		IV		IV																																	
			Day 1												8 Weeks																															
mFOLFOX 6 - 6 months Oxaliplatin, Leucovorin, 5FU	14 days	12 cycles	IV		IV		IV		IV		IV		IV		IV		IV		IV		IV		IV		IV		IV																			
			Day 1																				20 Weeks																							
Capecitabine only oral Capecitabine 2x daily for 14 days, then 1 week off	21 days	8 cycles	Oral		Oral		Oral		Oral		Oral		Oral		Oral		Oral		Oral		Oral		Oral																							
			Day 1																		18 Weeks																									
CAPEOX - 3 months Oxaliplatin infusion, day 1; oral Capecitabine 2x daily for 14 days, then 1 week off	21 days	4 cycles	IV		IV		IV		IV																																					
			Day 1												8 Weeks																															
CAPEOX - 6 months Oxaliplatin infusion, day 1; oral Capecitabine 2x daily for 14 days, then 1 week off	21 days	8 cycles	IV		IV		IV		IV		IV		IV		IV		IV		IV		IV		IV		IV		IV																			
			Day 1																		18 Weeks																									
5FU/Leucovorin Leucovorin and 5FU repeated weekly X 4-6, rest 2 weeks, start again	8 days	4 cycles	IV							IV							IV							IV																						

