4. STUDY MEASUREMENTS

Initial screening will take place via telephone. At the in-person baseline visit, after the patient signs the consent form, s/he will undergo a series of baseline assessments, questionnaires and blood draws as described above. Many of the data collection instruments will be either data entered by a researcher or self-administered by participants into REDCap, which is a secure web application for managing online surveys and databases. The table below provides an overview of the measurements that participants will undergo over the course of the protocol and the timing of these measurements:

Table 7. Measurement Schedule

Measure	Screening	Baseline	Weekly	PK Cohort Only	Post-Intervention Visit ³
Phone screening questions- PA screening and additional questions	X				
PAR-Q	X				
SF-36 ⁴		X			X
Demographics ⁴		X			
Paffenbarger questionnaire		X			X
Physical function tests (balance, gait speed, sit and stand, grip strength)		X			X
Food frequency questionnaire ⁴		X			X
Height, weight, waist and hip circumference		X			X
Whole body DXA		X		X ²	X
Patient-completed side effects questionnaires ⁴		X			X
D3- creatine dilution		X			X
NCI PRO CTCAE			X ¹		
Medical record review for chemotherapy dosing and toxicities			X		
Physical activity and nutrition logs			X		
Inflammatory markers		X			X
Pharmacokinetics (PK)				See section 4.14	
Injury history questionnaire ⁴					X
Intervention follow-up survey					X

¹ At each scheduled intervention visit (for intervention arm) and thereafter by phone or secure web-link every time chemotherapy appointment is scheduled. For U group controls, an RA will administer by phone or secure web-link every time a chemotherapy appointment is scheduled.

² For PK cohort, a DXA scan will also occur at time of 2nd PK draw, at approximately 4 months after initiation of the intervention

³ To be conducted within 2 weeks after last cycle of chemotherapy and end of intervention

⁴ As a result of COVID-19, to reduce in person time participants will complete baseline and post-intervention questionnaires virtually. Study staff will email participants a secure web-link, send them home with paper copies to be mailed back within 3 days, or administer questionnaires over the phone.

4.1 Screening questionnaire:

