Details of each patient's health history, including medical imaging, comorbidities and colon cancer diagnosis and treatment details will be extracted from the EMR. In addition, laboratory and clinical data about the colon cancer tumor marker Carcinoembryonic Antigen (CEA) and cardiometabolic risk factors blood glucose, lipids, blood pressure and medication usage conditions will be extracted from the EMR. See Appendix 13.2.1. A researcher will record all relevant medical variables in an online REDCap form. In addition, CT scans will be obtained from the participant's medical record. KP scans will be stripped of PHI and analyzed at DOR. Penn State and DFCI scans will be stripped of PHI and transmitted directly to DOR via SFT. CT scan closest to the date of diagnosis but before chemotherapy will be colored using TomoVision sliceOmatic software to determine body composition, including muscle attenuation.

4.10 Body composition and body size:

At the baseline visit and at the follow-up visit, a DXA scan to assess body composition will be performed (see Appendix 13.8.2). All DXA scans will be performed in the total body scanning mode. A third scan will take place after 4 months for the subset of people participating in the PK study to correspond to timing of the 2nd PK blood draws.

At the baseline visit and at the follow-up visit, d3-creatine dilution will be used to accurately assess total body skeletal muscle mass (see Appendix 13.8.3).

Height and weight will be assessed using a scale mounted stadiometer and digital scale (or per institutional clinic standards) to the nearest 0.1 cm and 0.1 kg. Waist circumference and hip

circumferences will be measured at standardized landmark with participants dressed in light indoor clothing without shoes. Height will be assessed at baseline only. A researcher will record anthropometric measurements in an online REDCap form. See Appendix 13.8.1.

Because of COVID-19, if a participant doesn't feel comfortable with study staff touching him/her for waist or hip circumference measures, the study staff can teach the participant how to self-measure while observing and recording results in REDCap.

4.11 Dose reductions/delays and early discontinuation of treatment:

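### The d3 creatine objective is stated at 6 months, but the only follow-up d3 measurement comes at the end of chemotherapy, which is about 3 months for 3-month regimens

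*Protocol*

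**What the plan says.** **The objective.** The protocol summary (objective 3a) and section 2.3.1 ask whether resistance training "increases d3 creatine muscle mass at 6 months". Section 9.1 repeats the time point: the aim is to "compare the effect of a RT intervention versus a wait-list control on d3 creatine muscle mass at 6 months".

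**The measurement.** Section 4.10: "At the baseline visit and at the follow-up visit, d3-creatine dilution will be used". Table 7 shows the same two occasions and no others. The extra 4-month scan in the pharmacokinetic cohort is DXA, not d3 creatine. Table 7, footnote 3, times the post-intervention visit: "To be conducted within 2 weeks after last cycle of chemotherapy and end of intervention".

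**The regimens.** Table 3 in section 3.7 includes a 3-month FOLFOX row and a row that begins "CAPEOX - 3 months Oxaliplatin infusion, day 1". Section 9.1 lists "duration of chemotherapy [3 months vs 6 months" among the minimization factors. The first intervention visit is to be "at the earliest possible chemotherapy visit but by the third infusion visit" (section 3.7), and the baseline visit is expected most often at the first or second infusion.

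**The length of participation.** Section 9.2: "Patient involvement and data collection will last approximately 6 months". Section 3.8, after Table 6, also puts the end of the intervention at about 6 months and equates that with finishing adjuvant chemotherapy. The SAP introduction instead ends the study two weeks past the final cycle and gives no number of months.

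**The analysis.** Section 9.3.3 describes d3 Aim 1 as a randomized comparison and names no covariates for it. SAP 2.2 puts all the minimization factors, treatment duration included, into the models for the primary endpoints.

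**The concern.** The objective names a fixed time, while the schedule fixes an event. The two agree only if everyone's chemotherapy lasts about 6 months, and the trial deliberately enrols patients for whom it lasts about 3.

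Length of training is part of what an effect on muscle mass means. If the pooled result is reported as a 6-month effect, readers will be told that patients trained for longer before measurement than many of them did. A small or null difference could then be read as no effect after 6 months of training, which the data could not show for 3-month patients because they have no 6-month d3 value.

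**Working it through.** **Inputs.** Cycle length and number of cycles come from Table 3. The visit window of up to 2 weeks comes from Table 7, footnote 3. For sLV5FU2 and weekly 5-FU/LV, the cycle-length column is not usable as printed, so the schedule described in the row is used: every 2 weeks for sLV5FU2; 4 to 6 weekly doses and then 2 weeks' rest for 5-FU/LV.

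**Formula.** End of last cycle (weeks from chemotherapy start) = cycle length × number of cycles. Latest visit = that + 2. Months = weeks / 4.35. No delays and no early stopping are assumed.

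| Regimen | End of last cycle | Latest visit | Months |
|---|---|---|---|
| FOLFOX, 6 months | 2 × 12 = 24 | 26 | 6.0 |
| sLV5FU2 | 2 × 12 = 24 | 26 | 6.0 |
| CAPOX, 6 months | 3 × 8 = 24 | 26 | 6.0 |
| Capecitabine | 3 × 8 = 24 | 26 | 6.0 |
| Weekly 5-FU/LV | (4 to 6 + 2) × 4 = 24 to 32 | 26 to 34 | 6.0 to 7.8 |
| FOLFOX, 3 months | 2 × 6 = 12 | 14 | 3.2 |
| CAPOX, 3 months | 3 × 4 = 12 | 14 | 3.2 |

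The first four rows reproduce the protocol's figure of about 6 months, counted from chemotherapy start. The last two rows do not come near it.

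**Interval between the two d3 measurements.** This is shorter when baseline falls after the first infusion. For 3-month FOLFOX, the second infusion is at week 2, so a baseline at the first infusion gives 12 to 14 weeks and at the second 10 to 12 weeks. Counting from a third-infusion start (week 4) gives 12 − 4 = 8 to 14 − 4 = 10 weeks, or 1.8 to 2.3 months. That is the latest permitted start of the intervention, so it is an extreme and not the expected interval from baseline.

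**Stated sensitivity.** Section 9.3.4 gives a detectable difference in mean change of 0.44 SD with 81 per arm: (1.960 + 0.842) × √(2/81) = 0.44. The figure reproduces, does not depend on visit timing, and is not in dispute. No d3-specific power is given.

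**Precision of estimates by duration.** With equal variances, and a share p of patients in a duration class, the standard error within that class is 1/√p times the pooled one: 1.15, 1.41 and 2.00 at p = 75%, 50% and 25%. The standard error of the arm-by-duration interaction is 1/√(p(1 − p)) times the pooled one: 2.0 at 50%, and 2.3 at 25% or 75%. These shares are assumptions, because the documents do not give the actual share.

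**The case against.** The best defence is that this is a matter of labelling. The visit itself is defined without ambiguity in Table 7, and section 3.8 shows that the authors use 6 months as shorthand for the end of chemotherapy. The d3 objectives stand apart from the primary and secondary ones, and no test, visit or sample size is wrong. Section 9.3.3 even lists time from chemotherapy start to assessment as a potential confounder in the longitudinal analyses, so the authors knew that timing varies.

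Much of this stands, and it is why the remedy is wording and one covariate. But the shorthand is true only of the longer regimens and cannot stretch to a visit at week 14. The confounder list serves d3 Aims 2 to 4, not the randomized Aim 1.

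Three further inferences are tempting, and the documents do not support them.

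- *6-month regimens are also measured short of 6 months.* Counted from a late start, some are. Weekly 5-FU/LV may run past 6 months, and the late-start count concerns the first exercise visit, not the usual baseline.
- *The plan dealt with duration for pharmacokinetics and neglected it for d3.* The second pharmacokinetic draw has to fall in a FOLFOX cycle at about 4 months (section 4.14), so restricting that sub-study to 6-month FOLFOX is a practical necessity and no parallel.
- *The SAP omits duration from the d3 model.* The SAP text available for this review lacks a part directly after the covariate and stratification paragraphs, so this cannot be asserted. What can be said is that protocol 9.3.3 names no covariates for d3 Aim 1.

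**Conclusion.** The stated time point is wrong for patients on 3-month FOLFOX or CAPOX. Their only follow-up d3 value falls by about week 14 from chemotherapy start, against about week 26 for most 6-month regimens. The design estimates an arm difference at the end of chemotherapy, averaged over the durations enrolled. The timing figures assume no delays; delays would move the visit later and early stopping would move it earlier.

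A reader might go on to infer that the comparison is biased. It is not on this account: planned duration is a minimization factor, so both arms should hold similar mixes of 3-month and 6-month patients. A reader might also infer that power is lost. That would require the share of 3-month patients and the effect at each duration, and neither is given. If, purely for illustration, 25% to 75% of patients are on 3-month regimens and their effect is between half of and equal to a 6-month effect of 0.44 SD, power with 81 per arm runs from about 42% to the full 80%. That range shows only that the documents do not settle the question.

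The correction is worth making because it changes what the trial can claim about a named objective. It does not touch the primary endpoints.

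**What to change.** 1. In objective 3a, section 2.3.1 and section 9.1, replace *at 6 months* with *at the end of chemotherapy (post-intervention visit)*.
2. In sections 3.8 and 9.2, replace *approximately 6 months* with wording that ties the length to the regimen: about 3 months for the shorter regimens, about 6 for most others, and possibly longer for weekly 5-FU/LV.
3. In section 9.3.3, state that the d3 Aim 1 model adjusts for planned duration (3 v 6 months) as recorded at randomization, in line with SAP 2.2 for the primary endpoints. Use planned duration, not actual duration, which may be affected by treatment.
4. Tabulate the weeks from baseline to follow-up d3 measurement by arm and planned duration, and do not call the pooled estimate a 6-month effect.
5. Optionally, show the arm difference by planned duration as a descriptive result. At assumed shares of 25% to 75%, it carries standard errors about 1.2 to 2.0 times the pooled one within a duration, and about 2.0 to 2.3 times for the interaction.

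The cost is wording in five places, one covariate that is already recorded, and one table. A true 6-month effect would instead need an added d3 visit for 3-month patients after their training had ended and after controls had been offered exercise materials (section 3.10). The SAP reports 183 participants already randomized, so correcting the label is the practical course.

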9.2.1 From Section D. Study overview of the original KPNC application approved 2017

3. How many participants will be enrolled in this study, or how many electronic records or medical records will be used? Provide your best estimate if you are not sure

Number of KPNC participants or records:	Approximately 115 participants to be enrolled
Records used:	Approximately 7500-KPNC records used
Number of non-KPNC participants or records:	Approximately 65 participants enrolled
Total number of participants or records:	Approximately 180* participants enrolled

**Due to the impact of the COVID-19 pandemic on the study, we estimate that the total number of participants will be within the range of 10% above the original total of 180 participants*

9.3 Statistical analysis:

9.3.1 Primary endpoints:

All data analyses will be by intent-to-treat, though in exploratory analyses we will consider compliance to intervention (defined as $\geq 75\%$ of planned sessions) and changes in MM. We will use multiple linear regressions to assess the difference between the intervention and wait-list control groups in mean relative dose intensity (RDI) for each agent and in mean average RDI (ARDI) across all agents. Continuous model covariates will be categorized either as quartiles or into clinically relevant categories (e.g. WHO BMI classification).

Analysis of number of grade 3 and 4 toxicities in relation to randomization arm will utilize Poisson regression given that this outcome can be characterized as a count. These regression models will provide point and interval estimates of adjusted proportional differences in rates of toxicities (expressed as rate ratios) between the control and intervention groups.

9.3.2 Secondary endpoints:

Analyses of inflammatory markers in relation to baseline body composition will utilize multiple linear regression techniques. These analyses of associations at baseline will be conducted in each randomization arm separately, followed by an analysis in the full sample (differences in associations at baseline across arms are not expected).

Pharmacokinetics: As 5-FU is known to undergo nonlinear disposition, compartmental modeling will be conducted using nonlinear mixed effects analysis with NONMEM (Icon Development Solutions, Hanover MD). NONMEM allows for simultaneous estimation of fixed-effects values (e.g. CL and V) and random-effects values (e.g. inter-individual, inter-occasional, and residual unexplained variability). Previous models of 5-FU and oxaliplatin²⁸ have been reported and will serve as a basis for development of the structural model. The final structural (e.g. 1- vs. 2-compartment) and error models (e.g. additive or proportional) will be chosen based on minimization of the objective function value (OFV, $-2 \log$ likelihood) and evaluation of diagnostic plots generated in R. During the covariate selection process, various measures of body composition (e.g. MM, MM/FM ratio) will be compared to identify the contribution of these parameters to PK variability in colon cancer patients. Pre- and post-intervention PK parameters (e.g. CL, V) will be compared using a paired t-test.

9.3.3 d3 creatine endpoints:

We will first assess the distribution of the baseline covariates by FORCE randomization arm. Most outcomes will be treated as continuous variables and we will fit linear regression models (e.g., for the continuous outcomes such as change in d3 creatine muscle mass, SPPB and SF-36 score, grip strength, relative dose intensity, and values of inflammatory markers, CEA and cardiometabolic risk factors). We will assess departures from regression model assumptions primarily by diagnostic plots of residuals, with attention to detection of non-constant variance of errors and detection of outliers that may indicate the need for a variance stabilizing transformation of the dependent variable. In secondary analyses, when considering outcomes dichotomously, we will fit logistic regression models (e.g., for abnormal CEA values).

Aim 1 is a randomized comparison of the FORCE resistance training intervention to the waitlist control. Analyses in Aims 2-4, however, are subject to confounding. Our *a priori*

set of potential confounders for cross-sectional analyses at baseline includes age, sex, body mass index or weight, race/ethnicity and tumor stage. For longitudinal analyses, potential confounders also include chemotherapy type, intervention assignment and time from surgery and/or chemotherapy start to assessment. We will include those covariates resulting in a 10% or more change in the d3 creatine muscle mass regression coefficient. The change-in-estimate approach to confounder selection performs well with regard to power, bias, mean squared error and confidence interval coverage.

9.3.4 Power:

Given previous exercise studies in cancer patients, we assume approximately 10% drop out with no follow-up DXA and blood draw for biomarker assessment. We expect chemotoxicity metrics (RDI, # toxicities) to be assessed on the full sample. We have sufficient power (.80) to detect a between arm difference in means of at least .42 standard deviation (s.d.) units (two-sided t-test, $\alpha=.05$) in Aim 1 analyses of chemotoxicity. With an expected RDI s.d. of 17.3⁴⁵, the minimum detectable difference in mean RDI is 7.3%, which is clinically meaningful and similar to effects found with a study of exercise among breast cancer patients receiving adjuvant chemotherapy⁴⁵. With the expected loss to follow-up and reduced sample size of 81 per group, the minimum detectable between arm difference in mean change is .44 units, which is considered in the “small” to “medium” range in effect size using the terminology and classification of Cohen. Relevant to Aim 4, on pharmacokinetics, a sample size of 30 subjects will provide sufficient power (.80) to detect a mean change of at least 0.5 s.d. units (two-sided t-test, $\alpha=.05$). Given previous data²⁶, the minimum detectable change in clearance of oxaliplatin or 5-FU due to RT is 15%.

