2. OBJECTIVE

2.1 Primary Objective:

To examine differences in dose reductions, dose delays and early stoppage for chemotherapy and the total combined number of moderate and severe chemotherapy-associated toxicities between intervention group and waitlist controls.

2.2 Secondary Objectives:

2.2.1 Examine specific inflammatory markers (CRP, IL-6, TNF- α receptor II [TNF-RII]) in relation to baseline MM and FM and examine differences in changes in inflammatory markers between intervention group and waitlist controls.

2.2.2 Examine the impact of intervention versus control and RT-induced body composition changes on the pharmacokinetics [PK] of 5-FU and oxaliplatin between baseline and 4 months of RT.

2.3 d3 Creatine Objectives:

2.3.1 Test whether resistance training during chemotherapy (FORCE intervention group v. control) increases d3 creatine muscle mass at 6 months.

2.3.2 Evaluate the association of d3 creatine muscle mass with changes in functional status and strength during chemotherapy.

2.3.3 Evaluate the association of d3 creatine muscle mass with chemotherapy toxicity and relative dose intensity.

2.3.4 Evaluate the association of d3 creatine muscle mass with cancer-related biomarkers, including inflammation, CEA levels and cardiometabolic risk factors.

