All participants will undergo measurements of inflammatory markers around the time of the baseline clinic visit and the follow-up clinic visit. Blood will be drawn at each time point in a standardized fashion. A total of three tubes of blood (one 8.5 ml SST red-top tube for serum and two 6 ml EDTA purple-top tubes for whole blood and plasma) will be collected from all participating patients.

Tubes will be prepared and stored at local sites until completion of study. Each site will maintain a log of all collected specimens. At the completion of the study, the participating institutions will submit that log to the coordinating center for verification that each participant had required samples. Upon completion of the study, samples will be shipped to the laboratory of [name], a FORCE PI at Dana Farber Cancer Institute, where his staff will inventory,

aggregate, and freeze samples until samples required for assays are shipped to [name] laboratory at Boston Children's Hospital. The combined log (with deidentified study ID and sample numbers only) will be submitted to respective testing labs to ensure all samples are received. Any additional or unused samples will be returned to and collectively stored at Dana Farber Cancer Institute until needed for future studies.

Collection and Processing

1 x 8.5 ml SST red-top tube will be collected at baseline and follow-up visit.

- Invert tubes 5 times to initiate clotting
- Allow blood to clot for a minimum of 30 minutes, but no longer than 2 hours.
- Centrifuge 15-20 min at 3000 RPM (1100-2000 x g) at room temperature or 4°C.
- Aliquot the serum (top layer) into 4 cryovials (800 ul aliquots) per tube of blood. Label as serum.
- Freeze samples at -70°C
- Batch ship on dry ice.

2 x 6 ml EDTA purple-top tubes will be collected at baseline and follow-up visit.

- Gently invert the tube 8-10 times to mix the EDTA.
- Centrifuge 1100-1300g for 10 min (swing-bucket) or 15 min (fixed-angle) at room temperature or 4°C.
- Aliquot the top layer (plasma) into 4 cryovials (800 ul aliquots). Label as plasma.
- Aliquot the bottom layer into 2 cryovials (800 ul aliquots). Label as buffy coat.
- Freeze samples at -80°C.
- Batch ship on dry ice.

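### The randomized comparisons of d3-creatine muscle mass and inflammatory markers name no baseline covariate; adding the participant's own baseline value would gain precision at little cost (minor)

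*Protocol*

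**What the plan says.** **d3-creatine.** Protocol 9.3.3 states that "we will fit linear regression models (e.g., for the continuous outcomes such as change in d3 creatine muscle mass" and other listed outcomes. It then says "Aim 1 is a randomized comparison of the FORCE resistance training intervention to the waitlist control". No covariate is attached to that comparison. The confounder list that follows is introduced for the association analyses (Aims 2-4) and does not contain the baseline d3-creatine value. Protocol 2.3.1 words the objective as muscle mass at 6 months.

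**Inflammatory markers.** Protocol 2.2.1 plans to "examine differences in changes in inflammatory markers between intervention group and waitlist controls", and Protocol 9.1 repeats the aim: "compare the effect of the intervention versus wait-list control on changes in inflammatory biomarkers". Protocol 9.3.2 describes only the baseline analysis: "Analyses of inflammatory markers in relation to baseline body composition will utilize multiple linear regression techniques". It then turns to pharmacokinetics. The nearest text to a between-arm analysis is Protocol 9.3.4, which gives a detectable difference in mean change of .44 SD with 81 per group and mentions no covariate.

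**Data available.** Protocol 4.10: "At the baseline visit and at the follow-up visit, d3-creatine dilution will be used to accurately assess total body skeletal muscle mass". Protocol 4.13: "All participants will undergo measurements of inflammatory markers around the time of the baseline clinic visit and the follow-up clinic visit".

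**Covariates elsewhere.** SAP 2.2 puts the five randomization factors into each model, under its heading for primary endpoints. It names no baseline value of an outcome. Protocol 9.3.1 says continuous covariates will be categorized.

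**Limit.** The SAP text available lacks a part between the end of section 2.2 and the references. Everything here refers to the text that could be read.

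**The concern.** When an outcome is measured before and after randomization, a model that includes the baseline value has a smaller standard error than an unadjusted comparison of change, unless the two measurements are almost perfectly correlated. The trial collects these baseline values and does not say it will use them in this way. At stake is how small a difference the secondary and d3-creatine comparisons can detect with about 81 participants per arm. The primary endpoints (RDI, ARDI and patient-reported toxicity) and the pharmacokinetic analysis are not touched.

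For the markers there is a second, smaller matter: the text does not say whether change is on the raw or the log scale. For the d3-creatine endpoints, transformation is left to residual diagnostics, including "detection of outliers that may indicate the need for a variance stabilizing transformation of the dependent variable".

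**Working it through.** **Inputs from the documents (Protocol 9.3.4).** Power .80; two-sided alpha .05 (stated for the chemotoxicity comparison, taken to carry over to the change comparison); 10% dropout, so 180 × .9 / 2 = 81 per group; detectable difference .44 SD of change.

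**Assumptions.** rho is not given, so a range of .3 to .9 is used. SDs are taken as equal at both visits. The 81 per arm is tied in 9.3.4 to follow-up DXA and blood markers; for d3-creatine it is assumed.

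**Step 1: reproduce the plan's figure.** Normal approximation: (1.960 + .842) × √(2/81) = .440. Exact t: .443. Power at .44 by exact t is .795. The stated .44 holds.

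**Step 2: effect of the baseline term.** With common variance s²:
- variance of change = 2s²(1 − rho)
- residual variance given baseline = s²(1 − rho²)
- ratio = (1 + rho)/2

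Estimating *k* covariate slopes multiplies the variance of the arm effect by about 1 + k/(N − k − 3), with N = 162. For the baseline term alone (k = 1) this is 1 + 1/158 = 1.0063.

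Example at rho .5: variance of the arm effect, in units of the change SD, is (2/81) × .75 × 1.0063 = .01864. The noncentrality is .44/√.01864 = 3.22 on 159 df, and power is .893.

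**Step 3: add the randomization factors.** They take 8 df (site 2, regimen 3, gender, stage and duration 1 each). If they explain nothing, the multiplier is 1 + 8/151 = 1.053 for a change score with factors, and 1 + 9/150 = 1.060 with baseline as well.

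| rho | (1+rho)/2 | .44 × √ratio | Detectable difference, exact t, baseline term only | Power at .44, baseline term only | Power at .44, baseline + factors |
|---|---|---|---|---|---|
| .3 | .65 | .355 | .358 | .931 | .918 |
| .5 | .75 | .381 | .385 | .893 | .877 |
| .7 | .85 | .406 | .410 | .853 | .834 |
| .9 | .95 | .429 | .433 | .812 | .792 |

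Comparators at .44: change score without covariates .795; change score with the factors .774. Simulation of 20,000 trials per rho gave .930/.894/.851/.811 for the baseline-only column.

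**Step 4: break-even against the unadjusted change score.** Baseline term alone: rho = 2/1.0063 − 1 = .987. Baseline plus factors, if the factors explain nothing: about .885.

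**Step 5: same estimand.** If follow-up = a + b·arm + c·baseline, then change = a + b·arm + (c − 1)·baseline. The arm coefficient b is identical, so the stated objective of comparing change is kept.

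**Illustration of scale.** The documents give no marker distribution. Suppose the markers are log-normal with SD of log .4 to 1.0 and rho .3 to .7, and the true effect is .44 SD of log change. Simulated power is then .42-.71 for raw change, .79-.80 for log change, and .85-.93 for log follow-up adjusted for log baseline. The contrast follows from placing the data and the effect on the log scale; it is not evidence about this trial's markers.

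**The case against.** **The plan is silent rather than wrong.** The d3-creatine model is introduced by an example, and an objective worded as muscle mass at 6 months fits a baseline-adjusted follow-up model equally well. Nothing forbids adjustment. The marker model may stand in the part of the SAP that could not be read. This stands, and it limits the point to a request for wording.

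**The gain may be nil for d3-creatine.** rho may be high for a muscle-mass measure. At rho .9 the baseline term adds under 2 points of power (.795 to .812). With the randomization factors added and explaining nothing, power is .792, just below the unadjusted .795. This also stands. However, against a change score carrying the same factors, the baseline term still gains (.774 to .792), and the factors may explain some variance.

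**A reader might infer that an open scale inflates the type I error.** That would require choosing raw or log by which is significant. The only transformation rule in the text, in 9.3.3, relies on residual diagnostics. A simulated choice by a residual normality test (4,000 null trials per setting, same SD and rho grid) rejected in .048-.058 of trials, which is roughly nominal. The documents do not support a claim of inflated error.

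**Conclusion.** Minor. On the text available, the d3-creatine comparison is illustrated as regression on change with no baseline covariate, and the marker comparison rests on an unadjusted mean-change power statement. A reader might infer a biased comparison or a wrong sample size. Neither follows: a change score is unbiased under randomization, and .44 SD with 81 per arm reproduces.

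The matter is precision on non-primary endpoints. For the baseline term alone, the gain at .44 SD runs from about 14 points of power at rho .3 (.795 to .931) to about 2 at rho .9 (.795 to .812). It is likely to matter more for the markers, if their rho is moderate, than for d3-creatine. These sizes rest on assumed rho, equal SDs and, for d3-creatine, an assumed 81 per arm.

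**What to change.** Add one sentence per endpoint to Protocol 9.3 or the SAP:

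- **d3-creatine muscle mass, intervention versus control:** regress follow-up (or change) on arm and the participant's baseline d3-creatine muscle mass, kept continuous.
- **CRP, IL-6 and TNF-RII, intervention versus control:** regress log follow-up (or log change) on arm and log baseline, kept continuous, with the log scale fixed before any unblinded analysis.

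State whether the five randomization factors are also included, in line with the SAP's primary models. State that the categorizing of continuous covariates in Protocol 9.3.1 does not apply to these baseline terms. Name the endpoint rather than the aim number, because Aim 1 means d3-creatine in 9.3.3 and chemotoxicity in 9.3.4.

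Cost: the wording, and one degree of freedom per model for the baseline term. The randomization factors, if included, take 8 more, worth about 2 points of power if they explain nothing (.795 to .774 for the change score). No new assessments or participants are needed.
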